Eligibility criteria will include 1) self-identify as Hispanic or Latino, 2) age 18 to 70 years, 3) receive primary care at one of the participating clinical sites, 4) at least one office visit within the previous 12 months to the primary care site, 5) diagnosis of T2D in the medical record, 6) T2D diagnosis for six months or longer, 7) most recent hemoglobin A1c \geq 8%, and 8) intention to continue to receive medical care at the recruitment clinic for the next six months. The value of 8% is higher than the goals established by the American Diabetes Association Guidelines (hemoglobin A1c<7%)⁹⁸, but lower than the definition of poorly controlled T2D established by the Center for Medicare & Medicaid Services Core Quality Measures Collaborative (hemoglobin A1c>9%)⁹⁹. It is common practice to increase an individual patient's goal hemoglobin A1c value in the context of clinical and social co-morbidities, but this goal value rarely exceeds 8%. Furthermore, the Minnesota Department of Health

has defined poorly controlled T2D as hemoglobin A1c \geq 8% for the purposes of mandatory reporting by clinical sites across the state¹⁰⁰. Therefore, we will use this value in keeping with common clinical practice to determine eligibility for the study.

The first step in screening for eligible participants is identification of Hispanic patients at both study sites with T2D. Per state-wide reporting mandates, each site maintains registries of their primary care patients with diabetes and the most recent hemoglobin A1c value for each patient. The second step in screening is to identify Hispanic adults within the subset of patients with the most recent hemoglobin A1c \geq 8% at both sites. Both sites have identified mechanisms for accurately identifying eligible patients (see letters of support). *In our pilot study, we identified 3,025 eligible patients across both sites.* Based on our pilot data, we expect to recruit approximately 50% women. Children were not included because of perceived community need that resulted in an intervention created for adults, and because of the relatively higher prevalence of T2D among adults.

Recruitment, Enrollment, Randomization, and Retention

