Once eligible patients are identified from institutional registries, the next office appointment for any diabetes-related indication (e.g., chronic disease management provider visit, diabetes educator visit, dietitian visit, diabetes group class, etc.) will be recorded for each patient. These patients will be contacted by telephone by a language-congruent study staff member to introduce them to the study and to assess preliminary interest in participation. Patients will be sequentially recruited at their next office visit until the target accrual is reached. Patients may also be recruited, consented and participate in study activities over the phone.

A language-congruent study staff member will confirm eligibility criteria with the patient and obtain written informed consent in an exam or private room before or immediately after their office appointment. Study staff will then obtain a baseline survey and biometric assessment (see measures) followed by randomization procedures (stratified by gender) and delivery of the digital storytelling intervention (for the intervention group). Each site has developed slightly different protocols for effective recruitment and intervention implementation based on lessons learned from the pilot study. Based on data from our pilot, we expect recruitment and enrollment to occur over a period of no more than 24 months across all sites with the following distribution:

- Hennepin Healthcare: N=240 participants enrolled.
 - Medicine Clinic
 - East Lake Clinic
 - Richfield Clinic
- Mountain Park Health Center: N=215 participants enrolled.

Participant retention will be facilitated in five ways. First, potential participants will confirm the eligibility criteria stating that they expect to receive medical care at the recruitment clinic for at least the next six months (above). Second, appointment cards for both subsequent study visits will be provided to participants after they have completed enrollment. Third, language-congruent study staff will contact patients by phone to remind them about upcoming study visits. Fourth, participants who do not return phone calls from study staff will be sent a letter asking them to call the study coordination to reschedule the appointment. Fifth, participants will receive remuneration at enrollment and at the of the 3 month visit.

Interventions

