Digital storytelling intervention. The digital intervention package, which is 12 minutes long, includes a brief introduction by an RHCP community partner, four stories with transitions, and a short closing educational message re-enforcing the four diabetes self-management behavioral goals (healthful diet, physical activity, medication adherence, glucose self-monitoring). The storytellers include two women and two men; they reflect some of the heterogeneity among Hispanic/Latino subgroups (two Mexican, one Central American, and one South American) in the U.S. After obtaining consent in the clinical setting or over the phone, study staff will deliver the intervention in the exam room, a separate private room or provide patient with a web address to view the video on YouTube from home.

Following the video exposure, study staff will ask these questions to each participant and record their answers: 1) What is your reaction to the video?, 2) What was the main message of the video, and 3) Does the video motivate you to make any changes to the way you manage your diabetes (probe positive responses)? These questions will confirm participant receipt of the intervention, which is an important fidelity construct to ensure that participants received and understood the intervention¹⁰¹.

Participants will be offered a copy of the video as a portable storage device (i.e., “flash drive”) for viewing on a computer, a DVD for viewing on a television, or a web address to watch the video on YouTube. Participants will also be provided access to the storytelling intervention as an application on their mobile phones and/or tablets. In our pilot of the storytelling intervention, all participants cited the use of mobile smart phones. Study staff will offer to assist participants in downloading this application during the baseline visit, and encourage participants to watch the video with family members or friends within their support network.

Figure 3. Still images from the existing digital storytelling intervention

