The control group will participate in the same usual clinical care for diabetes (e.g., visits with primary care physician, nurse, diabetes educator, dietitian, etc.) as the intervention group. We will control for study coordinator attention time throughout the enrollment and measurement activities. The control group will be offered the digital storytelling intervention package after the study is completed.

Measures

Participant data will be collected at baseline, six weeks, three months, and six months in their preferred language. Biometric measurements will be obtained during clinic visits at baseline and 3 months. The 3 month visit can occur up to 2 weeks prior to the visit due date and up to 4 weeks after the visit due date, to accommodate scheduling limitations during the COVID-19 outbreak. Participants will complete a survey (administered by same language-congruent study staff) to obtain secondary outcomes and theory-based measures (Table 2) at clinic visits or by phone within 2 weeks following the clinic appointment, and during phone calls at 6 weeks and 6 months. Surveys will be verbally administered to participants by bilingual research staff, and responses will be entered directly into an electronic database. Surveys are not printed and given directly to the participants to complete on their own. Participants will also receive appointment reminders (three total) prior to visits or calls.

Additional clinical data will be collected from the electronic medical records. Investigators and data analysts will remain blinded to group assignment throughout the study.

Demographic, health status, acculturation, health literacy, and diabetes knowledge measures. At baseline, study participants will report on the following demographic data: sex, age, ethnicity, country of birth, annual household income, education level, employment status and housing security. Individuals will report on the following proxies for acculturation: time lived in the U.S., primary language spoken at home, and level of English language proficiency on a 5-point Likert scale¹⁰⁷. Health literacy will be measured with the Short Assessment of Health Literacy—Spanish and English¹⁰⁸. Diabetes knowledge will be measured using the Diabetes Knowledge Questionnaire, available in Spanish and English¹⁰⁹.

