- Cholesterol values at 3 months will be drawn at the 3 month study visit. Recent values recorded as part of usual clinical care within two weeks prior to the visit may be abstracted from the electronic medical records.
- Subsequent cholesterol levels will not be drawn or abstracted.

The total volume of whole blood drawn from each participant will be approximately 8 mL (3 mL for hemoglobin A1C testing and 5 mL for cholesterol testing) when visiting the lab. Over-the-counter A1c Test kits will be mailed to patients unable to visit the lab. Study staff will call patients to confirm reception of kit and go through the instructions.

All study tasks can be completed in-person in the clinical setting, virtually, or a combination of both, to accommodate the growing interest of patients to perform tasks virtually, when possible. This flexibility is noted in the Study Tasks Table below.

The number of diabetes-related office visits will be abstracted from the electronic medical records and categorized as a visit with a primary care provider, endocrinologist, pharmacist, care manager, diabetes educator, dietician, community health worker or promotora. These visits will be recorded for the six-month interval before and after intervention (or control) delivery.

Theory-based measures. We will measure diabetes-related self-efficacy with the Diabetes Self-Efficacy Scale ($\alpha=0.85$)¹¹⁷, used in other studies with Spanish-speaking patients¹¹⁸, including one from our study team that we used to generate preliminary data for this proposal²². We will measure diabetes-related outcome expectations with the Outcome Expectancies Questionnaire¹¹⁹, and social support for diabetes with items from the Diabetes Care Profile¹²⁰, which we also used in our pilot study.

Story identification and transportation will be assessed through a 14-item scale developed by Larkey and colleagues that demonstrated very good construct validity among Hispanic, Spanish-speaking populations^{121,122}, with initial predictive validity on the transportation (emotional engagement) scale⁸⁴.

Intervention follow-up exposure. During follow-up measures, we will assess the number of times each participant viewed the digital storytelling videos and whether they viewed it with friends or family. This will provide an assessment of intervention dose for the intervention group following the supervised viewing at enrollment.

Table 2. Measures

Data Collected	Baseline	6 weeks	3 months	6 months

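### Shared viewing is encouraged but nothing keeps one household out of opposite arms, so some controls may see the video before the 3-month A1c and dilute the effect

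*Combined protocol and SAP*

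**What the plan says.** All references are to the combined protocol and SAP.

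- **Sharing is part of the intervention.** Under Interventions (Digital storytelling intervention), staff "encourage participants to watch the video with family members or friends within their support network". Participants are offered a flash drive, a DVD or "a web address to watch the video on YouTube", and they also get a mobile application.
- **The pilot points the same way.** In Preliminary data, Step 4, 25 of 25 viewers said they would show the video to relatives or friends who have diabetes.
- **Allocation is individual.** Under Recruitment, Enrollment, Randomization, and Retention, patients are recruited in sequence at office visits in the same clinics, and randomisation is stratified by gender only. No household-level allocation is described.
- **Eligibility does not mention households.** Study Participants lists eight criteria. One is that the patient must "receive primary care at one of the participating clinical sites". None concerns a relative or contact of someone already enrolled.
- **Controls are meant to be unexposed during the study.** Control Condition states: "The control group will be offered the digital storytelling intervention package after the study is completed".
- **Viewing is recorded.** Intervention follow-up exposure (under Measures) assesses the number of viewings for every participant, and Table 2 schedules this at 6 weeks, 3 months and 6 months without limiting it to one arm. The stated purpose is narrower: "This will provide an assessment of intervention dose for the intervention group following the supervised viewing at enrollment".
- **No allowance or analysis is planned.** Sample size considerations allows for about 12% loss to follow-up and nothing else. The Data analysis plan does not mention control exposure.

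**The concern.** The people with whom an intervention participant is most likely to share the video are relatives and friends with diabetes. Some of them attend the same clinics and may be in the trial as controls. The plan encourages the sharing and does nothing to keep such pairs apart.

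Two things follow. First, a control who views the video before the 3-month A1c may gain some of its effect, which shrinks the difference tested by the primary t-test. That matters because power is 80% only at 0.28 SD, and the plan's own expected range starts lower, at 0.25 SD. Second, relatives share diet, routines and often a clinician, so their A1c values are likely to be correlated, whereas the independent samples t-test treats every patient as independent.

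**Working it through.** **Inputs from the documents:** 200 evaluable per group; 0.28 SD; two-sided 5% independent samples t-test; stated power 80%; expected range 0.25 to 0.31 SD (all from Sample size considerations); 455 participants (Design Overview); and, in the pilot, "we identified 3,025 eligible patients across both sites" (Study Participants).

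**Assumed, not in the documents:** the share *c* of controls exposed before the 3-month A1c, and the fraction *f* of the full effect that an exposed control receives.

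**Step 1: reproduce the stated power.** The noncentrality is d × √(n/2) = 0.28 × √100 = 2.80. The normal approximation gives Φ(2.80 − 1.96) = Φ(0.84) = 80.0%, and the exact noncentral t gives 79.8%. The plan's 80% reproduces.

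**Step 2: dilute.** The observed effect is d × (1 − c × f). With f = 1, the upper bound, and d = 0.28:

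| Controls exposed | Effect (SD) | Power, exact t |
|---|---|---|
| 0% | 0.280 | 79.8% |
| 1.5% | 0.276 | 78.6% |
| 5% | 0.266 | 75.6% |
| 7.5% | 0.259 | 73.4% |
| 10% | 0.252 | 71.0% |

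At f = 0.5, 10% exposed gives 0.28 × (1 − 0.05) = 0.266 SD and 75.6% power, the same as 5% exposed at full effect.

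**Step 3: how far could relatives alone take it?** The share of the pool enrolled is 455 / 3,025 = 15.0%, and half of that, 7.5%, enters the intervention arm. Assume that relatives enrol independently of each other and that every intervention relative shares the video.

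- If 20% of controls have one eligible relative: 0.20 × 7.5% = 1.5% exposed.
- If every control has one: 7.5% exposed.

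These are the 1.5% and 7.5% rows above. Relatives who enrol together would raise the figure, as would sharing among friends.

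**Step 4: the plan's own range of effects, f = 1.** With 10% exposed, power falls from 70.3% to 61.2% at 0.25 SD, and from 87.1% to 79.5% at 0.31 SD.

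**Step 5: independence.** Relatives in the same arm raise the variance of the difference, and relatives in opposite arms lower it. Under individual randomisation either can occur, so the net effect on the test is probably small if few pairs enrol. The documents give no number of pairs or correlation, so it cannot be sized.

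**The case against.** The strongest case against is that this is mainly a design preference with a small consequence. The plan deliberately sits between efficacy and effectiveness, and social support is a hypothesised mediator, so family viewing belongs to the theory being tested. Nothing says that relatives will be enrolled; that they can be is an inference from the absence of a rule. With 15% of the pool enrolled, the household route alone costs little power. An exposed control would also miss the staff-led viewing and its follow-up questions, so full effect overstates the dilution. The bias runs toward no effect and cannot produce a false positive. Most of this stands, and it limits the size of the point. It does not remove the route, which the plan promotes and leaves unguarded.

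Three stronger readings are tempting, and the documents do not support them:

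- A reader might infer that viewing by controls will go unrecorded. The exposure paragraph covers every participant and Table 2 has no arm restriction. What is missing is a stated use of the answers in controls.
- A reader might infer that the video is publicly searchable on YouTube. The documents say only that an address is provided. The Dissemination and Sustainability Plan places public release after effectiveness is established, which suggests restricted access before then but does not prove it.
- A reader might infer that exposure could reach 20%, with power near 61%. The arithmetic is right, but no figure in the documents leads to that rate. It would need wide sharing among friends or relatives enrolling together.

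**Conclusion.** The concern holds in a limited form. The plan encourages a route to control exposure and has no household rule, no allowance and no analysis for it. The direction is known (toward zero) but the rate is not. Under the assumptions above, the loss at 0.28 SD is about 1 point of power at 1.5% exposed, 4 points at 5% and 9 points at 10%, with full effect in exposed controls as the upper bound. The household route alone plausibly lies toward the lower end.

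This does not threaten the validity of a positive result. It makes a null or small result harder to interpret, more so if the true effect is near 0.25 SD, where power is about 70% before any exposure. It is worth correcting because the correction is cheap and because control viewing is hard to reconstruct once follow-up has ended.

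**What to change.** 1. **Study Participants:** add that a person is not eligible if a member of the same household is already enrolled. This costs one screening question and a few relatives lost from a pool of 3,025 for 455 places. It also removes most of the independence problem. It does not reach friends, so items 2 and 3 are still needed.
2. **Interventions:** state that the YouTube link is unlisted and is issued only to intervention participants until follow-up ends. This is a link setting. An unlisted link can still be forwarded, so it reduces exposure without preventing it. Family viewing can continue.
3. **Intervention follow-up exposure and Table 2:** state that the viewing item covers both arms. Ask controls only after the 3-month A1c has been obtained, and record whether any viewing came before it. Asking earlier could prompt controls to look for the video; asking only at 6 months would rely on late recall for a 3-month endpoint.
4. **Data analysis plan:** pre-specify a supplementary complier-average (instrumental-variable) estimate, with randomised arm as the instrument and reported viewing before the 3-month A1c as the exposure. In its simplest form it is the intention-to-treat difference divided by the difference between arms in the proportion who viewed. For example, if all intervention participants and 10% of controls viewed, 0.252 / (1 − 0.10) = 0.28 SD. It assumes that allocation acts on A1c only through viewing, which the text messages may strain, and this should be said. It corrects the estimate for dilution but does not restore lost power. The intention-to-treat t-test stays primary.

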Rationale for implementation in the clinical setting. The work proposed in this application is intentionally placed on the boundary of the efficacy-to-effectiveness transition¹⁰² in clinical trials. We considered conducting a more traditional efficacy study, where participants would be invited to separate study visits for intervention delivery and measurements. However, interventions that target improvements in diabetes self-management behaviors cannot be easily disarticulated from the clinical setting. The hypothesized patient activation that may occur as a result of exposure to the digital storytelling intervention requires interaction with their healthcare home in order to translate that activation into improved outcomes. Therefore, we pilot tested the intervention in primary care-based clinical settings. We demonstrated feasibility of this approach while adapting intervention implementation for both sites.

Mobile short message service. Mobile short message service, i.e., text messaging, has been shown to have some impact on diabetes self-care¹⁰⁴ and cardiovascular-related lifestyle¹⁰⁵ behaviors. Furthermore, a Cochrane review suggested moderate evidence for increasing self-efficacy for diabetes self-management using mobile phone messaging¹⁰⁶. Therefore, to increase the likelihood that participants will watch the storytelling video several times during the intervention interval, participants will receive a monthly automated text message (five total) that asks them to self-rate their motivational level and self-efficacy for managing their T2D (0 = no motivation/self-confidence to 10 = extremely motivated/confident), and will recommend that they watch the storytelling intervention if they score lower than a 7. The rationale for the addition of mobile messages is that this intervention augmentation re-enforces concepts consistent with our theoretical framework. It increases

the potential treatment dose while maintaining an intervention package that is highly scalable. As stated above, our pilot data indicate ubiquitous smart phone use among potential study participants.

Control Condition

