The following data will be obtained at baseline from manual abstraction of the electronic medical records: date of diabetes diagnosis, diabetes medications, diabetes microvascular complications (nephropathy, retinopathy, neuropathy), and presence or absence of provider-assigned diagnoses of coronary artery disease, cerebrovascular disease, peripheral arterial disease, and hypertension.

Primary outcome measure. The primary outcome measure will be glycemic control as measured by hemoglobin A1c. The rationale for use of hemoglobin A1c as an indicator of diabetes control is based on national and regional data that demonstrate significant disparities in reaching hemoglobin A1c targets for Hispanic populations compared with non-Hispanic whites^{27,110}. The importance of glycemic control as part of the comprehensive management of diabetes is well documented, and hemoglobin A1c testing is a well-established strategy to monitor glycemic control in patients with diabetes¹¹¹. Hemoglobin A1c will be measured from whole blood samples obtained and analyzed in a blinded fashion by the clinical laboratories at Hennepin Healthcare and MPHIC; both laboratories use methods certified by the National Glycohemoglobin Standardization Program. Both laboratories are certified by the College of American Pathologists.

- Baseline hemoglobin A1c values will be drawn at the baseline study visit, abstracted from the electronic medical records, or reported from an self-check A1c test kit. A1c values drawn up to two weeks prior to the baseline visit date as part of usual clinical care may be used as the baseline A1c value.
- Hemoglobin A1c values at 3 months (primary outcome) will be drawn at the 3 month study visit, or abstracted from the electronic medical records, or reported from an self-check A1c test kit. A1c values drawn up to two weeks prior or 4 weeks after the 3 month visit date as part of usual clinical care may be used as the baseline A1c value.
- Hemoglobin A1c values at 6 months will be abstracted from the electronic medical records at both institutions. A1c levels drawn 5-7 months after the baseline value will be recorded.

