racial/ethnic minority populations, which showed a similar hemoglobin A1c reduction of 0.31 standard deviations¹²⁸. While these effects sizes are smaller than that of our pilot study, we have picked the more conservative (lower) estimate of effect size to ensure ample sample size. Hence, we can expect an effect likely to be between 0.25 and 0.31 standard deviation for the type of intervention proposed. Required sample sizes for an independent samples t-test to detect these two effect sizes, assuming 80% power, a two-tailed alternative and a 5% Type I error rate, are 252 and 145 patients per group, respectively. With 200 patients per group, we will have 80% power to detect an effect size of 0.28 standard deviations via the independent samples t-test. Accounting for approximately 12% loss to follow-up, we intend to recruit 225 patients in each group, for a total sample size of 450 participants.

Data analysis plan

Aim #1: Evaluate the efficacy of a community-derived digital storytelling intervention among Hispanic adults with poorly controlled T2D.

The primary analysis will be an independent samples t-test between the group average hemoglobin A1c values at 3 months. A two-sided alternative with a 5% type I error rate will be employed.

Supplementary analysis for the primary endpoint. Repeated measures modeling of the individual time point A1c values (including chart abstracted values at approximately 6 months) will allow for a more detailed investigation to the timing of the impact of the intervention by including all time points (including baseline). Profile analysis (Srivastava) will further assess for difference in overall means, time point, and treatment by time interactions. Covariates indicated above including demographics and clinical covariates will be included in the repeated measures and profile analysis models to assess the sensitivity of the primary analysis conditional on these potential concomitant (mediating) influences.

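### The 6-month A1c exists only where usual care happened to test, so the supplementary 6-month contrast can be biased in either direction; the 3-month primary test is unaffected

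*Combined protocol and SAP*

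**What the plan says.** All references are to the combined protocol and SAP.

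- **3-month A1c (Measures, Primary outcome measure).** The plan says "Hemoglobin A1c values at 3 months (primary outcome) will be drawn at the 3 month study visit, or abstracted from the electronic medical records", with a self-check kit as a third route.
- **6-month A1c (same section).** One route only: "Hemoglobin A1c values at 6 months will be abstracted from the electronic medical records at both institutions. A1c levels drawn 5-7 months after", with time counted from the baseline value.
- **Study contacts (Measures).** "Biometric measurements will be obtained during clinic visits at baseline and 3 months". Surveys are completed around the clinic visits "and during phone calls at 6 weeks and 6 months". The retention paragraph names payment at enrollment and at the 3-month visit, and none at 6 months.
- **Expected route of effect (Interventions, Rationale for implementation in the clinical setting).** The plan's reasoning is: "The hypothesized patient activation that may occur as a result of exposure to the digital storytelling intervention requires interaction with their healthcare home" if it is to become better outcomes. Diabetes visits are counted for six months before and after delivery.
- **Use of the 6-month value (Data analysis plan, Supplementary analysis for the primary endpoint).** "Repeated measures modeling of the individual time point A1c values (including chart abstracted values at approximately 6 months") is planned to study the timing of the effect, and a profile analysis is added. The primary analysis is a t-test on A1c at 3 months.

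No estimator, covariance structure or method for missing A1c values is named. Missing data appear only as an item in the statistician's monthly data checks.

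**The concern.** At 3 months the study can obtain the value itself. At 6 months it waits to see whether a clinician ordered a test. In usual care, a test plausibly depends on attending and on concern about control. If the video changes clinic contact, as the plan hopes, then having a 6-month value is a consequence of randomization. If testing is also related to A1c, the participants with values are no longer comparable between arms.

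Two results are exposed. The first is the 6-month A1c contrast, the plan's only glycemic evidence after the 3-month assessment. The second is the 3-month contrast inside the profile analysis. In its classical form that method needs a complete set of values per person, so participants without a chart test would drop out and take their 3-month data with them.

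**Working it through.** **The plan's own benchmark.** For 0.28 SD, two-sided 5%, 80% power: n = 2 × (1.96 + 0.84)² / 0.28² ≈ 200 per group (201 by the exact t calculation; 200 per group gives 79.8% power). The stated 200 reproduces, so 0.28 SD is a fair yardstick.

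**Is any 6-month draw hidden elsewhere?** The source statement, the biometric schedule, the phone contact and the payment schedule all agree that none is. Mailed kits are offered to patients who cannot reach the laboratory, but the A1c source list names kits for baseline and 3 months only.

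**Bias in observed 6-month values with no true effect.** The documents give no testing rates, so everything here is assumed:
- Y is the 6-month A1c in SD units, N(0,1) in both arms.
- P(tested | Y) = 1 / (1 + exp(−(a + bY))), with a chosen to give the stated testing rate p.
- Mean among the tested = E[Y × P(tested | Y)] / p, by numerical integration.
- Bias = that mean in the intervention arm minus that mean in the control arm. Negative values favor the intervention.

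| Intervention: rate, b | Control: rate, b | Bias (SD) |
|---|---|---|
| 70%, 0 | 50%, 0 | 0 |
| 70%, 0.3 | 50%, 0.3 | −0.058 |
| 70%, 0.5 | 50%, 0.5 | 0.143 − 0.236 = −0.093 |
| 70%, −0.5 | 50%, −0.5 | +0.093 |
| 70%, 0 | 50%, 0.3 | −0.147 |
| 70%, 0 | 50%, 0.5 | −0.236 |
| 60%, −0.3 | 60%, 0.3 | −0.235 |

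Unequal testing alone does no harm (first row). Reversing the signs of both slopes reverses the sign of the bias in any row.

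**What a likelihood model leaves.** Assume correlation ρ = 0.6 between every pair of time points.
- If testing depends only on the 3-month value, simulation gives a remaining bias of about 0.
- If testing depends on the 6-month value itself, baseline and 3-month A1c explain R² = 2ρ² / (1 + ρ) = 0.72 / 1.6 = 0.45 of its variance, so roughly 0.55 of the bias stays: 0.058 × 0.55 = 0.03, up to 0.236 × 0.55 = 0.13 SD. Simulation agrees.
- ρ is not in the documents. At ρ = 0.4 the fraction left is 1 − 0.32 / 1.4 = 0.77, so 0.04 to 0.18 SD. At ρ = 0.8 it is 1 − 1.28 / 1.8 = 0.29, so 0.02 to 0.07 SD.

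**Complete-vector profile analysis.** If testing depends on the 6-month value, the 3-month means of those kept shift by ρ times the 6-month shift: 0.6 × 0.058 = 0.03, up to 0.6 × 0.236 = 0.14 SD. This spurious 3-month difference would arise although the study has 3-month values for many of those dropped.

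**The case against.** The case on the other side has real force.

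- **The stakes are limited.** The primary t-test uses 3-month values and is untouched. The 6-month use is labeled supplementary, and its chart source is disclosed. This stands, and it sets the weight of the point.
- **Selection by arm is not in the documents.** A reader might infer that engaged patients will be tested in one arm and mainly patients of concern in the other. The plan does not say so. Both arms get the same usual care, all enter with A1c of at least 8%, and all intend to stay with the clinic for six months. The rationale paragraph makes dependence on arm plausible, and nothing more. The rows with slopes differing by arm are illustrations.
- **Bias need not favor the intervention.** A reader might infer a spurious benefit. The sign depends on who gets tested, and the effect could equally be masked.
- **A1c is not the only durability evidence.** Self-management behaviors, self-efficacy, outcome expectations and social support are surveyed by study phone call at 6 months. The gap concerns A1c only.
- **Repeated-measures modeling may already help.** It would, if fitted by likelihood with all available values, but the plan does not commit to that. Nor does it say that the profile analysis drops incomplete vectors; that loss is conditional on the classical form being used.
- **Kits might be used at 6 months.** The Measures section allows virtual completion and points to a study tasks table that is not in the text available. The A1c source list does not include this route. If it is intended, the list should say so.

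**Conclusion.** The concern holds for the supplementary 6-month A1c contrast, and for the profile analysis if it uses complete vectors. It does not reach the primary analysis.

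Under assumed testing models with no true effect, the observed-value bias is 0 when testing is unrelated to A1c, about 0.06 to 0.09 SD in either direction for 70% vs 50% tested with a common slope of 0.3 to 0.5 log-odds per SD, and about 0.24 SD when slopes differ by arm. A likelihood model with baseline and 3-month A1c lowers this to about 0, or to 0.03-0.13 SD, depending on which value drives testing. The last range rests on the assumed correlation of 0.6. The upper values are large enough, against 0.28 SD, to mislead a statement about durability. The documents support the possibility of bias. They fix neither its direction nor its size.

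**What to change.** Amend the supplementary analysis paragraph of the Data analysis plan:

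1. Keep all time points, since the stated purpose is timing. Fit a likelihood-based mixed model that includes everyone with any A1c value, in place of a complete-vector profile analysis.
2. Report by arm the proportion with a value in the 5-7 month window, with the baseline and 3-month A1c of those who have one and those who do not.
3. Add a delta-adjusted sensitivity analysis: shift the missing 6-month values by amounts fixed in advance, separately by arm and in both directions, and report where the conclusion changes. The mixed model alone cannot deal with testing that depends on the unobserved 6-month value.
4. Label the 6-month A1c contrast exploratory and make no durability claim from chart values alone.

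Settle this before group assignments are unblinded. The cost is a few sentences, one descriptive table and one further analysis, all on A1c values the plan already collects, plus a more cautious 6-month statement. Obtaining the 6-month A1c by study procedure would address the cause, at the price of another draw or kit per participant; the changes above do not depend on it.
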